  ELSE IF <baseline IGA>=2 THEN DO;
    IF <IGA per week primary endpoint> < 0.5 THEN <IGA 0/1 response> =1;
    ELSE IF <IGA per week primary endpoint> >=0.5 THEN <IGA 0/1 response> =0;
    ELSE PUT "E" "RROR:" stysid1a=;
  END;
  ELSE <IGA 0/1 response> =0;
RUN;
```

The treatment differences for each imputed data set will then be evaluated by exact logistic regression and ODDS ratio as described in [Section 5.1.2.2](#). This analysis will be done by `_IMPUTATION_` for the comparison to the placebo treatment group. The model should be estimating response probability = 1 by using DESECENDING option. Using the EXACT statement in the GENMOD procedure and the ODS OUTPUT data set “ExactOddsRatio” provides the exact estimate for the odds ratio and confidence intervals.

```
PROC GENMOD <option>;
  CLASS <stratum> <treatment>(ref="")/ param=ref;
  MODEL <response> = <explanatory variables> / link=logit dist=bin type3;
  BY <by-variables>;
  EXACT <treatment>/ ESTIMATE=both ;
  ODS OUTPUT ExactOddsRatio =Estimates;
RUN;
```

The MIANALYZE procedure expects the parameter estimate in the variables ESTIMATE. No standard error estimate for odds ratio will be provided in “Estimates” dataset.

```
Data <modified dataset>;
```

```
set Estimates;
ESTIMATE=Estimate;

if missing(ESTIMATE) then delete;
RUN;
```

The estimates and standard errors of the log (odds ratio) based on the 100 imputed data are then combined by applying Rubin's rules for multiple imputed data sets, see [Little and Rubin \(2002\)](#).

Programming notes:

- The variables ESTIMATE in the input data set for the MIANALYZE procedure may not be missing. Records with missing values need to be deleted and the variable \_IMPUTATION\_ needs to be renumbered and regenerated since for each by group the procedure expects consecutive numbers starting at 1.
- The ESTIMATE and STDERR in terms of odds ratios from logistic regressions will be transformed to follow a normal distribution before MIANALYZE procedure. They will be transformed back to Odds Ratio to get the corrected ESTIMATE and corresponding CIs.

The SAS procedure MIANALYZE will be applied as follows:

Step 1:

```
DATA <modified dataset_t>;
SET <modified dataset>;
stderr= stderr;
VARIABLE="estimate";
RUN ;

ODS LISTING CLOSE;
ODS OUTPUT ParameterEstimates=<results> VarianceInfo=<varinfo> ModelInfo=<modelinfo>;
PROC MIANALYZE PARMS=<modified dataset>;
BY <by-variables>;
MODELEFFECTS ESTIMATE;
RUN;

ODS LISTING;
data <results_back>;
set <results>;

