estimate=exp(ESTIMATE);
LCLMEAN=estimate*exp(-1.96*stderr);
UCLMEAN=estimate*exp(+1.96*stderr);
RUN ;
```

In case if exact logistic regression does not converge and risk difference estimates will be provided. The SAS procedure PROC FREQ for risk difference estimates will be applied as follows:

```
ODS LISTING CLOSE;
PROC FREQ DATA=<Imputed dataset> ORDER=DATA;
  TABLES <treatment group>*<response variable>/riskdiff fisher alpha=0.05;
  BY <By-variables>;
  ODS OUTPUT RiskDiffCol1=RiskDiffCol1 FishersExact=fisherexact;
RUN;

ODS LISTING;
DATA DRISK; SET RiskDiffCol1;
  WHERE control="1";
  ESTIMATE=risk;
  STDERR=ase;
  effect="Riskdiff";
```

```
IF missing(ESTIMATE) OR missing(STDERR) THEN DELETE;  
RUN;  
  
PROC SORT DATA=DRISK; BY <By-variables>; RUN;  
ODS LISTING CLOSE;  
ODS OUTPUT ParameterEstimates=results VarianceInfo=varinfo ModelInfo=Modelinfo;  
PROC MIANALYZE PARAMS=drisk;  
  by <By-variables>;  
  modeleffects Riskdiff;  
  stderr ase;  
RUN;  
  
ODS LISTING;  
DATA results2;  
  set results;  
  or=estimate*100;  
  lowercl=(LCLmean)*100;  
  uppercl=(UCLmean)*100;  
  KEEP <response variable> <By-variables> or lowercl uppercl probt;  
RUN;
```

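### SAP 5.1.2.3: the template code for the primary multiple-imputation analysis does not carry out the pooling its text states, and no single p-value under imputation is named for H1-H6

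*SAP*

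**What the plan says.** Multiple imputation is the primary missing-data method for the PASI and IGA response variables (SAP 2.6.4), with 100 imputations (SAP 5.1.2.3). The model is exact logistic regression (Protocol 9.4.2; SAP 2.6.3).

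**Pooling, SAP 5.1.2.3.** The text reads: "The estimates and standard errors of the log (odds ratio) based on the 100 imputed data are then combined by applying" Rubin's rules. A programming note adds: "The ESTIMATE and STDERR in terms of odds ratios from logistic regressions will be transformed to follow a normal distribution before MIANALYZE procedure". The code requests "EXACT <treatment>/ ESTIMATE=both" but saves only "ODS OUTPUT ExactOddsRatio =Estimates", and the SAP comments: "No standard error estimate for odds ratio will be provided in" that data set. It then calls "PROC MIANALYZE PARMS=<modified dataset>" and back-transforms with the line that begins "estimate=exp(ESTIMATE".

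**P-values.** SAP 5.1.2.2 bases every reported p-value on a regression coefficient on the GENMOD exact test, halved for a one-sided test when the effect favours secukinumab. SAP 2.7.2 says only that one-sided p-values are derived, and tests at alpha/2 = 1.25% per dose.

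**Fallbacks.**
- Non-convergence: SAP 2.6.3 and 5.1.2.2 drop covariates and end in Fisher's exact test. SAP 5.1.2.3 gives a pooled risk difference.
- A 0% or 100% response rate: SAP 2.6.3 gives a risk-difference p-value under imputation and Fisher's test under non-responder imputation. SAP 5.1.2.2 says the odds ratio and p-value are not shown.
- Missing estimates, SAP 5.1.2.3: "Records with missing values need to be deleted and the variable" that indexes the imputations is renumbered.

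**The concern.** These passages govern the confirmatory tests of PASI 75, IGA 0/1 and PASI 90. A programmer cannot follow the code and the text of 5.1.2.3 together. Even with the code repaired, the SAP does not say which number is compared with 1.25%: an exact p-value, of which there are 100 per hypothesis, or the pooled Wald-type p-value. The two can fall on opposite sides of the boundary. When the model fails to converge, the SAP names two different tests.

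The Document History logs an update to the imputation, exact-regression and risk-difference code after the Week 24 database lock. Protocol 5.4 has designated sponsor staff unblinded from that lock. A reader of the results therefore needs to know which rule was applied.

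**Working it through.** **1. Text against code in SAP 5.1.2.3.**
- Scale: the text pools log odds ratios. The code sets the estimate equal to itself and no line takes a log.
- Standard error: the text pools standard errors. The saved table has none by the SAP's own statement, and the code sets `stderr` equal to itself.
- Data set: the code builds `<modified dataset_t>` but gives `<modified dataset>` to MIANALYZE.
- Back-transformation: `exp()` is applied to a quantity that was never logged.

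As printed, no pooled standard error can be formed. If one were supplied, the scale would be wrong. At the planned IGA rates the odds ratio is (0.45/0.55)/(0.10/0.90) = 7.36, its log is 2.00, and exp(7.36) is about 1,578.

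**2. Deciding p-value.** Exact tests on 100 data sets give 100 p-values and no rule combines them. The pooled parameter table saved in the odds-ratio block would hold one p-value, but later lines use only the estimate and limits. Only the risk-difference block explicitly keeps its p-value (`probt`).

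**3. The plan's own power figures.** Inputs from SAP 3 and Protocol 9.7: 40 per arm, one-sided 0.0125, placebo against secukinumab 10% v 65% (PASI 75), 10% v 45% (IGA 0/1) and 8% v 39% (PASI 90). With a placebo and c secukinumab responders,

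power = sum over a, c of Bin(a; 40, p0) x Bin(c; 40, p1) x [p(a,c) <= 0.0125].

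Fisher's test gives 0.9991, 0.8837 and 0.8211, which reproduces the stated 99%, 88% and 82%.

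**4. Log-odds rule on the same tables.** z = ln[c(40-a)/(a(40-c))] / sqrt(1/a + 1/(40-a) + 1/c + 1/(40-c)), with the SAP 2.6.3 risk difference where a cell is empty.

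Boundary example, 13 v 4 responders of 40:
- log odds ratio = ln(13 x 36/(4 x 27)) = 1.466
- SE = sqrt(1/4 + 1/36 + 1/13 + 1/27) = 0.626
- z = 2.343, one-sided p = 0.0096, against an exact p of 0.0134

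At 14 v 4 the exact p is 0.0072, so the exact test needs one more responder.

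| Endpoint | Exact power | Log-odds power | Verdicts differ |
|---|---|---|---|
| PASI 75 | 0.9991 | 0.9996 | 0.05% |
| IGA 0/1 | 0.8837 | 0.9133 | 3.0% |
| PASI 90 | 0.8211 | 0.8610 | 4.0% |

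Every difference is a rejection by the log-odds rule that the exact test does not make. A stratified check used three assumed age-by-weight splits per arm (10/4/10/16, 7/3/12/18, 12/4/12/12), equal rates across cells, no baseline PASI and 40,000 simulated trials each. It gave 2.6-2.7% (IGA 0/1), 3.1-3.4% (PASI 90) and 0.04-0.06% (PASI 75).

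**5. The two fallbacks.** For 6 v 0 of 40, the risk difference is 0.15 with SE sqrt(0.15 x 0.85/40) = 0.0565, so z = 2.66 and p = 0.0039. Fisher's p is 0.0128. The two fall on opposite sides of 0.0125.

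**6. False-positive rate.** At common response rates of 2% to 20%, the log-odds rule with its fallback rejects with probability 0.0005 to 0.0085 and Fisher's test with 0.00001 to 0.0055. Both are below 0.0125. A risk-difference test used in every trial would reject 1.46% at 10% v 10%, above nominal. The SAP uses it only as a fallback, so that is not the plan's error rate.

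**The case against.** The code blocks are templates with placeholders. The text names the right scale twice, and the confidence-limit lines (estimate times exp of plus or minus 1.96 standard errors) make sense only for log odds ratios. A value near 1,578 or a missing standard error would show up on the first run. This stands: the stated method is sound and the slips are correctable.

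The exact-test sentence in 5.1.2.2 can be read as the rule for one data set, with pooling afterwards. That is reasonable, but it leaves the test of H1-H6 unnamed and sits badly with a sentence that covers all p-values.

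For 0% or 100% response, 5.1.2.2 may only suppress the regression output while 2.6.3 supplies the replacement. That reading works, but the SAP does not state it. For non-convergence, the split in 2.6.3 between multiple and non-responder imputation may explain Fisher's test against the risk difference. That link is only implied.

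The percentages compare two tests on complete data, without baseline PASI or the etanercept arm. They measure the gap between candidate rules, not the effect of the coding slips.

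Three stronger readings are tempting but not supported:
- *Suppressed p-values cost power.* This treats an undisplayed p-value as a failed test, although 2.6.3 provides one for that case.
- *Empty cells would remove most imputations.* Records are deleted only if the estimate is missing, and nothing in the SAP says an empty cell makes an exact estimate missing.
- *The rule was changed after unblinding.* The same sections were also updated before the lock, and what changed afterwards cannot be seen.

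**Conclusion.** The point holds and should be fixed. In SAP 5.1.2.3 the template code and the text cannot both be followed, the p-value that decides H1-H6 under imputation is not named, and the non-convergence rules name different tests. The 0%/100% rules can be reconciled but need a sentence saying so.

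The gap between the exact and log-odds rules is about 3.0% of trials for IGA 0/1, 4.0% for PASI 90 and 0.05% for PASI 75. This assumes the planning rates, 40 per arm, one-sided 1.25%, no missing data and no covariates. PASI 75 is practically unaffected.

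A reader might infer that the reported odds ratios or p-values are wrong. The documents do not show that: they give no results and do not show the program that was actually run.

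**What to change.** 1. **SAP 5.1.2.3, code.** Save the exact parameter estimate on the log-odds scale with its standard error; the option already in the template is meant to request it. Pass that data set to MIANALYZE and exponentiate once.
2. **SAP 5.1.2.2 and 5.1.2.3, p-value.** Name the pooled log-odds p-value, one-sided, as the test of H1-H6 under multiple imputation, and limit the exact-test sentence to analyses without it. Record the rule actually used at Weeks 24 and 52. Show beside it the exact analysis with non-responder imputation, which SAP 2.6.5 already plans.
3. **Fallbacks.** Cross-refer 2.6.3, 5.1.2.2 and 5.1.2.3 so that one fallback applies under multiple imputation and one under non-responder imputation. Say what is done when only some of the 100 data sets have an empty cell.

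The cost is SAP wording, program notes and a short record, with no new data. Because the Week 24 and Week 52 analyses precede this SAP version, the change documents the rule and does not pre-specify it.

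The downside is that the pooled log-odds rule is less conservative than the exact test: against 4/40 it needs 13 responders rather than 14. It also makes the deciding test Wald-type, although Protocol 9.4.2 names exact logistic regression and the sample size rests on Fisher's test.

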### 1.1 Study design

This is a multicenter, randomized, double-blind, placebo-and active-controlled (etanercept in single blinded arm) study in pediatric subjects aged 6 years to less than 18 years with severe chronic plaque psoriasis. Approximately 160 subjects aged 6 years to <18 years will be enrolled, of which at least 30 pediatric subjects will be 6 years to <12 years old. In reality around 40-45 patients will be needed to meet the requirement of recruiting about 30% of subjects in the < 25kg weight group.

Subjects will be randomized using a 1:1:1:1 ratio into one of the treatment arms: secukinumab low dose, secukinumab high dose, etanercept or placebo. The randomization will be stratified by age (<12 years or ≥12 years) and weight (<25 kg, 25-<50 kg, ≥50kg) at randomization. Subjects randomized to the placebo group will be pre-assigned to either the low- or high-dose group of secukinumab, at the Randomization visit, in case they are not achieving a PASI 75 response as assessed at Week 12.

The study consists of 5 Epochs: screening (up to 4 weeks), induction (of 12 weeks), maintenance (of 40 weeks), extension treatment epoch (open-label of 184 weeks) and post-treatment follow-up epoch (of 16 weeks). The detailed information of the study design is described in [Figure 1-1](#).

**Figure 1-1** Study design

The following study periods will be considered for analysis:

- **Screening period** (before Randomization)
- **Induction period** (Randomization to Week 12 pre-dose), including follow-up period (F4, F8, F12 and F16 (EOF) visits) for prematurely discontinued subjects before Week 12 completion. For placebo PASI 75 responders at Week 12, subjects will enter follow-up period after Week 12, including the first visit F4 and four weeks later visit EOF at F8.
- **Maintenance period** (Week 12 dose to Week 52 pre-dose), including follow-up period (F4, F8, F12 and F16 visits) for prematurely discontinued subjects before Week 52 completion, and for etanercept patients with the completion of the maintenance epoch.
- **Extension period** (Week 52 dose until Week 236 (EOT)), including follow-up period (F4, F8, F12 and F16 visits) for prematurely discontinued subjects before Week 236 completion.
- **Entire treatment period** (Randomization to Week 236 (EOT)), for safety analysis, exposure including follow-up period up to last dose + 84 days.
- **Entire study period** (Randomization to end of study (EOS)), including follow-up period (F4, F8, F12 and F16 visits).

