## 2 Statistical methods

## 2.1 Data analysis general information

This document covers the statistical analysis plan for Week 24 PEA analysis, Week 52 analysis and final analysis.

█████ will perform the analyses at week 24 and week 52 and final analysis. Statistical software SAS version 9.4 or later will be used.

Summary statistics for continuous variables will be presented with n, mean, standard deviation, minimum, lower quartile (Q1), median, upper quartile (Q3) and maximum for observed values and change from baseline. Summary statistics for discrete variables will be presented in contingency tables and will include absolute and relative frequencies.

P-values will be presented as one-sided for hypothesis testing and as two-sided for other analysis. Two-sided 95% confidence intervals will be displayed. If not otherwise specified, hypothesis testing will be based on one-sided p-values that the treatment effect is in favor of secukinumab. The level of significance will be set to 2.5% (one-sided, family-wise type-I-error). The 95% confidence intervals will not be used for decision making; they will only be used for estimation and will therefore always be two-sided.

All listings will be presented by treatment sequence.

Footnotes will generally be provided for

- abbreviations used in the output; abbreviations used on several outputs, e.g. for listings can be presented on a separate page and do not have to be repeated as footnotes on each listing
- sort order of categories, e.g. for sorting within MedDRA (Medical Dictionary for Regulatory Activities) hierarchy levels
- MedDRA version used for reporting of MedDRA coded data

Footnotes will generally NOT be given for

- units displayed on the output
- interpretation of results (e.g. “odds ratio larger than 1 favors active treatment”)
- information that can be retrieved from the statistical section of the CSR unless it is not identifiable from the output, e.g. explanation of analysis model used unless results of more than one model are displayed on an output
- derivations of variables (e.g. body mass index (BMI) will not be explained in a footnote)
- information that will be provided in the clinical study protocol and/or methods section of the CSR (e.g. baseline definition if this is specified in the statistical section of the CSR)

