### 3 Sample size calculation

Approximately 160 pediatric subjects from 6 to less than 18 years of age, with 2 subgroups: 6 to less than 12 years of age, and 12 to less than 18 years of age. Stratification is planned for age (<12 years,  $\geq$ 12 years) and weight (<25kg, 25-<50kg and  $\geq$ 50kg). It will be targeted to have at least 30 subjects in the <12 years subgroup at a minimum. Enrollment of children aged 6 to less than 12 years will proceed after efficacy and safety data for approximately 80 (approximately 40 treated with AIN) enrolled adolescents (aged 12 to less than 18 years) treated for 28 weeks have been reviewed and deemed satisfactory by a Data Monitoring Committee.

Since two secukinumab dose regimens will be tested versus placebo with respect to the coprimary endpoints (PASI 75 response and IGA 0 or 1 response at Week 12), the type-I-error will be split to 1.25% one-sided for each comparison. With 40 subjects per group and assuming a response rate of 10% for PASI 75 response and IGA 0 or 1 response in the placebo group, the power to show a response rate of 65% for PASI 75 response and 45% for IGA 0 response in the secukinumab groups based on Fisher's exact test (nQuery Advisor 7.0, two group Fisher's-exact test of equal proportions) is approximately 99% for PASI 75 response and approximately 88% for IGA mod 2011 0 or 1 response. For the secondary endpoint of PASI 90 response at week 12, assuming a response rate of 8% in the placebo group, the power to show a significant difference between a secukinumab dose and placebo, assuming a response rate of 39% in the secukinumab groups based on Fisher's exact test (nQuery Advisor 7.0, two group Fisher's-exact test of equal proportions) is approximately 82% for PASI 90 response. The assumed response rates for secukinumab are based on the confirmatory efficacy in severe patients in the adult phase III program. At Week 12, PASI 75 response rates of 11% and PASI 90 response rates of 7% have been reported in the placebo group in [Paller et al \(2008\)](#) for children and adolescents aged 4-17 years.

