### 5.1.2.2 Exact Logistic regression

Selected binary outcome variables including PASI 50 / 75 / 90 / 100 response and IGA mod 2011 0 or 1 response, will be evaluated using an exact logistic regression model with treatment regimen, age category, baseline body weight category and baseline score for the response variable. Remove “baseline score for the response variable” from the exact logistic regression model, if model doesn’t converge or have insufficient SAS memory issue while executing the model. Odds ratios will be computed for comparisons of secukinumab dose regimens versus control(s) utilizing the exact logistic regression model fitted.

Additional exact logistic analysis will be performed for IRT dosing error subjects, using both multiple imputation and pure non-responder imputed records.

If response rates are 0% or 100% in one of the treatment groups then odds ratio estimates and p-values will not be displayed in outputs, but “-” will be shown.

The odds ratio will be calculated such that an odds ratio  $> 1$  is favorable for secukinumab. Using PROC GENMOD with EXACT statement to calculate the confidence interval for the odds ratios conditional on all other parameters specified in MODEL statement. The 95% confidence interval for the regression parameter of the active treatment effect relative to control(s) will be calculated using an exponential transformation to create the confidence interval for the odds ratio.

All p-values reported on linear hypotheses about regression coefficients will be based on the exact tests in the SAS procedure PROC GENMOD with EXACT statement.

For superiority hypotheses, one sided p-value will be calculated by dividing the two-sided p-value by half (i.e., “p/2”) if treatment effect is in favor of secukinumab dose regimens and calculated by “1-p/2” if treatment effect is in favor of Control.

Exact logistic regression will be applied to response variables at each visit.

If exact logistic regression model does not converge, then the following steps will be performed:

- If convergence not reached, remove the covariates from the model one by one until convergence is reached; start with continuous covariates (i.e., baseline PASI), followed by removing categorical covariates (i.e., age, bodyweight strata);
- If convergence not reached at all, then perform Fisher’s exact test.

It should be noted that this model might not converge if response rates are too low.

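### SAP 5.1.2.3 drops imputations without an exact-logistic estimate before pooling, so if only some fits fail, the pooled odds ratio rests on a non-random subset of the 100

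*SAP*

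**What the plan says.** SAP 5.1.2.3 sets 100 imputations, fits the exact logistic regression separately in each, and combines the log odds ratios by Rubin's rules. Both the code and a programming note cover a missing estimate. The note reads "Records with missing values need to be deleted" and then has `_IMPUTATION_` renumbered consecutively from 1. The text still presents the combined result as coming from all 100 imputed sets. No minimum number of usable imputations is set, there is no refit, and nothing requires the number lost to be reported. The risk-difference code at the end of the section has a similar line: "IF missing(ESTIMATE) OR missing(STDERR) THEN DELETE".

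SAP 5.1.2.2 gives the expected reason for failure: "It should be noted that this model might not converge if response rates are too low".

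The SAP also has other routes for difficult fits:

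- **2.6.3 and 5.1.2.2:** remove covariates one at a time, then use Fisher's exact test.
- **5.1.2.2:** drop the baseline score if the model does not converge or memory runs out; show no odds ratio if a group has 0% or 100% response.
- **2.6.3:** under multiple imputation, when a group has 0% or 100% response, report the risk difference with a t-test.
- **5.1.2.3, end:** a pooled risk difference if the exact model does not converge.

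None of these says whether it applies to a single imputation or to the whole analysis, or whether it comes before the deletion.

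**The concern.** Rubin's rules average over all the draws. If the model fails more often in sets with few imputed responders, the surviving sets are chosen by the outcome being estimated, and their average no longer estimates what the full set of draws would. After renumbering, the pooling step treats the survivors as a complete set. The interval uses a fixed 1.96, so a small number of survivors is not reflected in the degrees of freedom.

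The code deletes estimate records, not whole imputed data sets. The low-dose and high-dose contrasts could therefore be pooled over different imputations.

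This pooling step serves both co-primary endpoints, PASI 90 and the by-visit comparisons with placebo.

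**Working it through.** **Planning inputs (SAP 1.1, 2.1 and 3).** Allocation: "Subjects will be randomized using a 1:1:1:1 ratio into one of the treatment arms". Error rate: "The level of significance will be set to 2.5% (one-sided, family-wise type-I-error"), of which "the type-I-error will be split to 1.25% one-sided for each comparison". Sample size: "With 40 subjects per group and assuming a response rate of 10"% on placebo, against "65% for PASI 75 response and 45% for IGA 0 response in the secukinumab groups". For PASI 90 the rates are 8% and 39%.

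**Reproducing the plan's power.** Exact enumeration of Fisher's test with 40 per arm at one-sided 0.0125 gives:

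| Endpoint | Stated | Recomputed |
|---|---|---|
| PASI 75 | about 99% | 99.9% |
| IGA 0 or 1 | about 88% | 88.4% |
| PASI 90 | about 82% | 82.1% |

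The planning inputs are therefore read correctly.

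**How often would the placebo arm be empty of responders?** With n children and response rate p, P(0) = (1 − p)^n.

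| Setting | n | p | P(0) |
|---|---|---|---|
| Co-primary, planned rate | 40 | 10% | 0.90^40 = 1.5% |
| PASI 90, planned rate | 40 | 8% | 0.92^40 = 3.6% |
| Sparser endpoint or visit (assumed rate) | 40 | 5% | 0.95^40 = 12.9% |
| Sparser endpoint or visit (assumed rate) | 40 | 2% | 0.98^40 = 44.6% |
| Under 12 years | 8 to 11 | 10% | 0.90^8 = 43% to 0.90^11 = 31% |
| Under 12 years | 8 to 11 | 8% | 0.92^8 = 51% to 0.92^11 = 40% |

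The last two rows take the minimum of 30 children under 12 and the 40 to 45 mentioned in SAP 1.1, divided by four arms (7.5 to 11.25). SAP 5.1.2.3 applies multiple imputation to PASI 50, 75, 90, 100 and IGA 0 or 1 by visit. SAP 5.1.2.2 applies the exact model to the subgroups without stating their imputation method; I assume the primary one.

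**What deletion would do if triggered.** These assumptions are not in the documents: no observed placebo responder, m placebo children missing at Week 12, each imputed as a responder with probability q, and no estimate returned when placebo has no responder. The expected share deleted is (1 − q)^m:

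- m = 1, q = 2%: 0.98 = 98% deleted, about 2 sets left.
- m = 2, q = 5%: 0.95² = 90% deleted, about 10 left.
- m = 4, q = 10%: 0.90⁴ = 66% deleted, about 34 left.

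Take 26/40 responders on secukinumab (0.65 × 40) and no covariates. The exact conditional odds ratio is 96.0 with 0 placebo responders (median-unbiased estimate), 68.2 with 1 and 33.4 with 2. For m = 2 and q = 5% the weights are 0.9025, 0.095 and 0.0025.

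- All sets kept: exp(0.9025 × ln 96.0 + 0.095 × ln 68.2 + 0.0025 × ln 33.4) ≈ 93.
- After deletion: exp[(0.095 × ln 68.2 + 0.0025 × ln 33.4) / 0.0975] ≈ 67.

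For m = 4 and q = 10% the same calculation gives about 82 with all kept and 61 after deletion. With 18/40 (0.45 × 40), the two cases give about 42 against 30, and 37 against 27. Deletion pulls the odds ratio toward 1 here.

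**Does the SAP's own fallback stay finite?** For 26/40 against 0/40 the risk difference is 0.65, with standard error √(0.65 × 0.35 / 40) = 0.075. The risk difference can therefore be computed in a set with no placebo responders.

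**The case against.** The strongest reply is that the deletion may never act. If every fit gives an estimate, all 100 are pooled as the text says. A reader might infer that the primary odds ratio does rest on a selected subset. The documents do not support that: they report no failed fits, and at the planned rates an empty placebo arm is uncommon.

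Second, nothing in the SAP says that zero placebo responders produce a missing estimate. Section 5.1.2.2 says only that the model might fail at low response. An exact analysis can return a finite median-unbiased value at the boundary, as the calculation above does. If the software returns it, the deletion shares above do not apply.

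Third, the fallbacks exist, including a risk-difference rule written for multiple imputation at 0% or 100% response. SAP 2.6.5 also repeats the co-primary and PASI 90 analyses under pure non-responder imputation, where nothing is pooled. The pooling code saves model and variance output, so the loss could be traced; what is lacking is a duty to report it.

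All of this stands, and it limits the size of the problem. It does not settle the mixed case, in which some imputations fail and others do not. Applied to single imputations, the fallbacks would yield Fisher p-values or risk differences that cannot be averaged with log odds ratios. Applied to all 100, they would leave the deletion little to do. The SAP does not choose between these, and the only explicit instruction on a missing estimate before pooling is to delete it.

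**Conclusion.** The point holds in conditional form. If the exact model fails in some but not all imputations for a contrast, the stated rule pools a subset selected on the imputed responses, and that subset may differ between the two doses. If no fit fails, the result is unaffected.

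For the co-primary endpoints and PASI 90 at the planned rates the sparse case is uncommon (1.5% and 3.6% for an empty placebo arm of 40). It is more plausible at early visits, for PASI 100 and in the age or weight subgroups. SAP 4.1 records that some Week 12 visits fell after Day 88, outside the primary window, so missing Week 12 values are plausible; neither their number nor their arm is given. The actual effect cannot be computed from the documents, and the odds ratios above only illustrate direction and order of size.

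Two further inferences should be resisted. The deletion is not shown to favour secukinumab: in the scenario worked here it is conservative, although a conservative direction does not make the pooled estimate or interval valid. Nor do the documents show that any test conclusion would change.

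**What to change.** 1. Remove the delete-and-renumber instruction from SAP 5.1.2.3, and the matching deletion line in the risk-difference code.
2. State the order once, in 2.6.3, and refer to it from 5.1.2.2 and 5.1.2.3: if the exact model gives no estimate in any of the 100 imputations for a contrast, apply the existing fallback to all 100 before pooling. That means the reduced covariate set first, then the pooled risk difference already described in 2.6.3 and 5.1.2.3. Reserve Fisher's exact test for the non-responder analysis, where there is nothing to pool.
3. Report the number of failed fits for each contrast, endpoint and visit.

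The exact model in protocol 9.4.2 need not be replaced by another estimator, because the SAP's own fallback is enough. The cost is a few sentences and a few lines of code, with no new data. The downside is that sparse contrasts would show a less adjusted odds ratio, or a risk difference in place of an odds ratio.
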